Although the ICTs care for patients over the age of 18,¹⁰ most of the patients referred to ICTs are older – in January 2017, 61% were aged 75 or over and only approximately 5% were aged under 50.¹¹ They tend to have long-term conditions, complex care needs or are approaching the end of their life.

The ICT models were launched in all localities on 27 July 2015, at which time their core teams were in place and they were ready to see referred patients. The ICT models were not prescriptive and developed organically in each locality (Farnborough, Farnham, Yateley, Fleet and Aldershot), to best meet the local needs. For example, anecdotally, two of the ICTs, in Farnborough and Aldershot, are getting more referrals for patients with mental health issues, while another, Farnham, may be seeing more patients with dementia.

By April 2017, a total of 885 patients had been referred to ICTs across the five localities.¹² By June 2017, 1,051 patients had been referred. Although all the ICTs were launched in July 2015, they have developed at different paces, with varying levels of referrals (Figure 1). In January 2017, 25 new patients were referred in Farnborough, 19 in Farnham, 19 in Yateley, 12 in Fleet and 9 in Aldershot.⁶ This is equivalent to between 0.04% and 0.1% of the local population, depending on the locality.⁶ Over time, the Vanguard is aiming to expand to the top 2% of patients in need.

Figure 1. Number of patients referred to ICTs each month in each of the five localities

Source: NEHF CCG

Up to June 2017, patients were predominantly referred to the ICTs based on a clinical judgement, rather than through the application of pre-defined eligibility criteria. The majority of referrals came from GPs, though referrals were also received from other health care workers (eg community staff, mental health, social care).¹⁰ For example, it has been reported that in January 2017, 84 patients were referred to ICTs across the 5 localities, of which 53 were referred by GPs (63%), 14 by community staff, 11 by social care staff, 1 by mental health staff and 1 from the Medically Fit for Discharge list from Frimley Park Hospital.

Only four of the patients referred in January 2017 were reportedly identified from the predictive modelling tool Johns Hopkins ACG [Adjusted Clinical Groups] system.^{6,13}

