Proportion of deaths in hospital will be used as a proxy for patients dying in their preferred place of death. While patients may not die in their preferred place outside of hospital, it is assumed for the purposes of this analysis that locations outside of hospital (e.g. home, care home, hospice) would always be preferred over dying in hospital. Proportion of deaths is calculated by combining information on hospital deaths from the SUS data with information on all deaths from the NHAIS data.

Delayed transfers of care will not be evaluated, as the IAU does not have access to reliable data.

Variable definitions

Bedding-in period and study period

The ICTs were launched on 27 July 2015 across all five NEHF localities. Although the ICTs developed their capacity and services at different rates across the five localities, they were running services immediately. This study will not include a bedding-in period (i.e. a period omitted from the analysis to allow time for the interventions to become established). Although the earliest start date for the intervention group is 27 July 2015, the study period will start in mid-July 2015 (the exact date being the date of the NHAIS monthly extraction) to allow for potential control patients to be included from that date.

The study period will end mid-June 2017 (the exact date being the date of the NHAIS monthly extraction). During this period, most of the patients referred to ICTs were selected based on clinical judgement.

Exposure variable

A person is considered to be in the intervention group (i.e. exposed to the intervention) if they were registered with a NEHF general practice and referred to an ICT between 27 July 2015 and mid-May 2017. By only including patients referred up to mid-May 2017, the IAU allows for at least one month of exposure to the intervention. Persons in the intervention group will be identified from the list of referred patients, supplied in pseudonymised form from NEHF CSU.

Index dates and follow-up period

Each patient will be followed up within the study period for a length of time specific to that patient. A patient's follow-up period will start from the index date, which is defined as:

- If the patient was referred to the ICT, then the date of their first referral. For the purpose of this analysis, this is the date at which they are considered to have started the intervention.

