- If the patient was not referred to the ICT (i.e. in the potential control group), then monthly potential index dates will be assigned, starting from the latest of the following:
 - the study period start date (see section on Bedding-in period and study period, p. 23)
 - date of earliest registration with a general practice in NEHF CCG, set as the date of the extraction in which they are first known to have been registered with a general practice in NEHF.

If a patient was referred more than once, only the first date is used, that is, if patients were discharged and then subsequently referred again, they are treated as though they stayed on the ICT register. No differentiation will be made between active or dormant patients (see section on Integrated care teams, p. 12).

For potential control patients, monthly index dates will be assigned from mid-July 2015 up to mid-May 2017. As the first and last monthly dates may be based on extraction dates (see

above and below), the dates set for all other months will for consistency also correspond to the extraction date of the corresponding month. This will also enable more accurate information on whether a patient was a care home resident at the index date, which is one of the potential covariates (see section on Baseline variables, p. 25).

A person's follow-up period ends when the person either dies, moves from NEHF CCG or the study period ends. Thus, the end date is defined as the earliest of the following dates:

- the end of the study period, that is mid-June 2017, set to the date of the last available NHAIS extract
- date of death, set to the date of the extraction in which death is first recorded
- date of de-registration from CCG general practice, set to the day before the date of the extraction in which they were first registered with a general practice outside NEHF.

A person's follow-up period may therefore be between approximately 1 and 23 months.

The date of death is estimated as the extraction date of when they were first recorded as having died. However, as the true death date could be as early as the day after the previous extraction date, there is a risk that the follow-up period is overestimated by up to a month, during which time the patient would have no recorded hospital activity. However, as it is unlikely that the day of the month that a person dies is other than random, this is unlikely to introduce bias between the intervention and control groups.

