Appropriate baseline variables will be included in both the matching and the regression models. All baseline variables are calculated on pre-period data. Potential baseline variables to include in the matching or as covariates in the modelling are listed in Table 3.

Table 3. Potential baseline variables

Category	Variables at patient level
Demographics & socio-demographics	
 • Approximate age at index date • Gender • Ethnicity • Average socioeconomic deprivation deciles, based on the Index of Multiple Deprivation (IMD) 2015, available at layer super output area (LSOA) level • Urban/rural classification at lower LSOA level, based on the 2011 census
Prior hospital use	
 • Number of emergency admissions in the last 60 days of the pre-period • Number of emergency admissions in year -1, the last year of the pre-period (i.e. 365 to 1 day before index date) • Number of emergency admissions in year -2 of the pre-period (i.e. 730 to 366 days before index date) • Number of ACS emergency admissions in the last 60 days of the pre-period • Number of ACS emergency admissions in year -1 of the pre-period • Number of ACS admissions in the year -2 of the pre-period • Number of elective admissions in year -1 of the pre-period • Number of A&E attendances in year -1 of the pre-period • Number of outpatient attendances in year -1 of the pre-period • Number of missed outpatient visits in year -1 of the pre-period • Average length of stay in year -1 of the pre-period
Health variables	
 • Elixhauser list of comorbidities, identified in the pre-period • Specific comorbidities linked to frailty, identified in the pre-period³⁰ • Other comorbidities predictive of hospital emergency admission, as identified in the Inpatient Outpatient A&E and GP(IPOPAEGP) model,³¹ identified in the pre-period

	
 • Number of Elixhauser comorbidities in the pre-period • Number of frailty comorbidities in the pre-period
Support	
 • Resident in a nursing or residential home
Time period	
 • Index date/period (quarter & year, e.g. q1y1, q2y1...)
Level of care available	
 • Locality in which the patient is registered with a GP

All comorbidities will be defined using data from any diagnosis field in any hospital admission in the pre-period.

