- 1.0 a table for showing study length and reasons for censoring (leaving the study).

Data cleaning and validation checks

Data cleaning and data validation checks will be performed by the IAU Data Management team, in accordance with the IAU Data Management Quality Assurance Process. Where appropriate, a summary of the results can be produced for the technical appendix.

Data flow diagrams

The following diagrams will be produced for the technical appendix:

- 1.0 data linkage process diagram
- 2.0 data flow diagram of study cohort selection.

5. Addendum

This section has been added to the original statistical analysis protocol (SAP) document to provide further clarifications and information on modifications to the original SAP. The original SAP was agreed in September 2017 with this section added in July 2018.

Definition of study cohort, page 18

In addition to the exclusion criteria described on page 18 of this document, the following exclusion criteria were applied prior to the analysis:

- Patients with no valid Lower Layer Super Output Area (LSOA) geographic area – this variable was used to determine a patient’s level of socioeconomic deprivation
- For potential control patients, patients more than 2 years’ older than the oldest ICT patient or more than 2 years’ younger than the youngest ICT patient – this was to limit the size of the dataset of potential controls in the matching process

Study endpoints, page 21

Here we provide further clarification on how variables were defined.

Elective admissions are defined as those that are ‘ordinary’ or day cases and exclude maternity and regular day/night cases.

When calculating readmission rates, the NHS Outcomes Framework guidance⁵⁶ was followed, with the exception of also including elective day cases as potential offsets for the calculations. This was consistent with the definition of elective admissions described above, which includes both ‘ordinary’ and day cases.

For the variable average length of stay in the year prior to the index date, any hospital spell that starts in the pre-period but continues into the follow-up period was included in its entirety within the pre-period. For the outcome measure average length of stay in the follow-up period, we only included spells that both start and finish within the follow-up period. There is no expected bias between the ICT and matched control groups, as both had access to the same hospitals.

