The IAU identified a number of ‘overlapping’ in-patient spells (stays) in the SUS data where, for example, a patient spell with one provider did not end before a spell with another provider started. When calculating average length of stay, we did not account for these overlapping spells. Instead, the average length of stay was calculated for each spell, as recorded in the data. Note: For the outcomes emergency bed days and elective bed days, bed days were not double-counted, that is the number of unique days in hospital following either emergency or elective admission were calculated.

Duplicate outpatient appointments were removed. Outpatient appointments relating to mental health services, to the extent these were recorded in the outpatient data, were included.

Index dates and follow-up, page 24

To further limit the size of the dataset of potential controls, only one potential index date per quarter was created for potential patients aged less than 65 years. Only 14% of ICT patients in the study were younger than 65 years.

Baseline variables, page 26

The variables mental ill health and serious mental ill health, as defined on page 32, were included as baseline variables, replacing the mental health definition specified in IPOPAEGP.

Connective tissue disease in the IPOPAEGP was not included as a baseline characteristic, as it overlapped with the Elixhauser definition of rheumatic arthritis. The Elixhauser variable peripheral vascular disorders was not included in error.

Identifying control group, page 28

Due to low numbers of care home residents that were referred to ICTs (<10), matching on type of residence (ie whether a person lived at home, in a nursing or a residential care home) was not done by exact matching.

Matching parameters, page 29

Due to the size of the dataset of potential control patients (approximately 750,000 records), the parameters for the genetic matching algorithm was limited to iterations based on population size 200, maximum generation 100 and number of generations to wait 10.

Statistical analysis, page 30

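### Follow-up starts at referral for ICT patients but on calendar dates for controls, and no baseline variable captures time since discharge within 60 days or being in hospital at the index date

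*Protocol*

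**What the plan says.** The Protocol section on index dates and follow-up sets the two clocks differently. For the intervention group the rule is: "If the patient was referred to the ICT, then the date of their first referral". For the comparison pool: "For potential control patients, monthly index dates will be assigned from mid-July 2015 up to mid-May 2017". These dates follow the registration data, since "the dates set for all other months will for consistency also correspond to the extraction date of the corresponding month". The addendum thins them further: "only one potential index date per quarter was created for potential patients aged less than 65 years".

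Table 3 lists the candidate baseline variables. The shortest windows are "Number of emergency admissions in the last 60 days of the pre-period" and the matching count for ambulatory care sensitive admissions. The table also has counts of emergency and ACS admissions for each of the two preceding years, elective, A&E and outpatient use and average length of stay in the last year, and the index quarter. The addendum's core adjustment list adds a two-month count of urgent care sensitive admissions. No entry gives days since the last discharge or says whether the patient was in hospital at the index date.

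Under Diagnostics, balance is judged on the listed baseline variables. The section on choice of matching variables says that probably only some of them will enter the matching algorithm.

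**The concern.** A referral date is chosen by a clinician for a reason. An extract date is fixed by the calendar and has no link to the patient's course. If referrals tend to come soon after a discharge, ICT patients enter follow-up at a higher-risk moment than controls with the same 60-day count. The risk of a new emergency admission is assumed here to be highest just after discharge and to fall afterwards.

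Equal counts do not cure this, because a count over 60 days carries no information on where in the 60 days the event fell. The standardised differences would look good whether or not the timing differed. The affected outcomes include emergency admissions, a primary endpoint, and the error would make the ICTs look worse than they are. Follow-up can be as short as about one month, where such a difference weighs most.

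This differs from the confounding that the protocol describes as unobservable. Admission and discharge dates are in SUS, and the protocol already uses them to calculate length of stay.

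**Working it through.** The protocol gives no figure for time from discharge to referral and no event rate, so there is nothing of its own to reproduce on size. Two of its facts bear on the premise. In January 2017, 53 of 84 referrals came from GPs (53/84 = 63%, as stated), and "1 from the Medically Fit for Discharge list from Frimley Park Hospital" (1/84 = 1.2%).

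**Assumed inputs**
- Share *p* of each group with an emergency discharge in the last 60 days: 20% or 40%, equal in both groups, so the 60-day counts balance.
- Hazard relative to later, for days 0–13 / 14–29 / 30–59 since discharge: 3/2/1.5, or a milder 2/1.6/1.2.
- Time since discharge for those controls: uniform over 0–59 days.
- Time since discharge for those ICT patients: all within the last 14 days, or half within 14 days and half uniform.
- No true effect of the ICTs.

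**Formula.** Let H be the sum of the daily relative hazards over T days of follow-up, averaged over the starting day. Patients without a recent discharge contribute T. The rate ratio with no effect is

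RR = [p·H(ICT) + (1−p)·T] / [p·H(control) + (1−p)·T].

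**Upper case** (p = 40%, 3/2/1.5, all within 14 days):
- T = 90: H(control) = 110.88, H(ICT) = 136.00. RR = (54.40 + 54.00)/(44.35 + 54.00) = 108.40/98.35 = 1.10.
- T = 274: H(control) = 294.88, H(ICT) = 320.00. RR = (128.00 + 164.40)/(117.95 + 164.40) = 292.40/282.35 = 1.04.

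**Lower case** (p = 20%, 2/1.6/1.2, half within 14 days):
- T = 90: H(control) = 99.90, H(ICT) = 106.50. RR = (21.30 + 72.00)/(19.98 + 72.00) = 93.30/91.98 = 1.01.
- T = 274: H(control) = 283.90, H(ICT) = 290.50. RR = (58.10 + 219.20)/(56.78 + 219.20) = 277.30/275.98 = 1.00.

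| p | ICT discharges | Multipliers | 3 months | 6 months | 9 months |
|---|---|---|---|---|---|
| 40% | all within 14 days | 3/2/1.5 | 1.10 | 1.05 | 1.04 |
| 40% | half within 14 days | 3/2/1.5 | 1.05 | 1.03 | 1.02 |
| 20% | half within 14 days | 3/2/1.5 | 1.03 | 1.01 | 1.01 |
| 20% | half within 14 days | 2/1.6/1.2 | 1.01 | 1.01 | 1.00 |

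**Cross-check with a smooth hazard**, b[1 + (k−1)exp(−t/τ)]. Here k is 2 or 4, τ is 30 or 60 days, and 20% or 50% are recently discharged. Mean time since discharge is about 10 or 17 days for ICT patients against 30 for controls. The ratio is 1.02–1.21 at 1 month, 1.01–1.13 at 3 months and 1.00–1.05 at 12 months.

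Both forms agree: under these assumptions equal 60-day counts leave a bias against the ICTs that fades as follow-up lengthens.

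**The case against.** The strongest reply is that the premise is not documented, and this stands. A reader might infer that an admission or discharge triggered the referral. The protocol says only that referral was mostly by clinical judgement, often after a discussion with the patient. One of 84 referrals in a month came from a hospital discharge list, and 20% of patients referred by the end of February 2017 had no admission in two years. Referral source does not settle timing, since a GP may refer soon after a discharge, but the protocol gives no interval.

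A reader might also take the addendum's rule that "any hospital spell that starts in the pre-period but continues into the follow-up period was included in its entirety within the pre-period" as evidence that ICT patients were in hospital at index. It is a rule for counting spells, does not separate the groups, and shows no imbalance. Any patient in hospital at index cannot be newly admitted until discharged, which partly offsets the bias.

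Nor do the 60-day counts alone align the groups. Annual counts, A&E use and index quarter also help. Several candidate dates per control, in a pool of about 750,000 records, make it possible to match to controls with a recent admission, though less so under age 65.

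Finally, the protocol warns plainly about unobserved reasons for referral and doubts the constant-rate assumption behind its offset. That disclosure is fair, but it does not cover a timing variable that the data already hold. Patients with short follow-up also contribute little person-time, which limits the effect on the pooled estimate.

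**Conclusion.** The point holds in a limited form. Index dates arise differently in the two groups, nothing listed measures recency within 60 days or inpatient status at index, and the planned balance checks would not reveal a difference in either.

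Whether ICT patients were in fact nearer their last discharge is not known from the document. If they were, the rate ratio for emergency admissions is pushed upwards by about 1–10% at 3 months and 0–4% at 9 months, under the main set of assumptions above. The 10% figure needs 40% of patients to be recently discharged and every such ICT patient to fall within 14 days. With only half of them within 14 days it is 1–5% at 3 months. No separate size was worked out for 30-day readmissions or A&E attendances.

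It would go too far to conclude that the results are biased by a known amount, or that discharge dates would remove confounding by referral. A trigger seen only in primary or community care would leave ICT patients at higher immediate risk with no difference in discharge timing. The case for acting is that the check is cheap and deals with an observable part of the problem.

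**What to change.** Derive two variables from the SUS dates already held:
- days since last emergency discharge at the index date, in bands 0–7, 8–30, 31–60, 61–365 and none in the last year;
- in hospital at the index date, yes or no.

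Add both to Table 3, the balance table and the regression adjustment. Offer the first to the genetic match without requiring an exact match. Show event rates by month since index in each group, so that an early excess that fades can be seen.

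The addendum indicates that the match has already been run. In that case, report both variables by group and add them to the adjusted models, at least as a sensitivity analysis.

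Do not require an exact match on inpatient status. Exact matching on residence was abandoned because fewer than 10 care home residents had been referred, and a rare status within five localities is likely to fail in the same way. Do not restart follow-up at discharge for these patients: a control who was not in hospital has no discharge to start from, and in-hospital deaths would be lost.

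The cost is two derived variables and refitted models. If the match is re-run, balance on other variables may be slightly harder to reach.
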